## **4. OVERALL STUDY DESIGN**

The study is a parallel group multicenter randomized controlled trial (RCT), comparing the effects of a 'DBT-based group therapy' (DBT-bGT) /structured skills training group treatment with 'Treatment as usual' (TAU) for adults with ADHD.

**Fig. 1 Trial flow-chart**

In an uncontrolled extension phase of the initial 14 week trial, participants initially receiving TAU will be offered the DBT-based group treatment. All participants will be re-assessed at follow-up 6-months after ended DBT-bGT.

Study Period: Estimated date of first patient enrolled: December 2015  
Anticipated recruitment period: 1 years  
Estimated date of recruitment end: 31/12/2016  
Estimated date of last patient completed follow-up: 15.05.2017

Treatment Duration: The DBT-based group therapy (DBT-bGT) /structured skills training group treatment lasts for 14 weeks, and thereafter participants will be re-assessed at follow-up 6-months after. Those of the participants receiving initial TAU conditions will have an additional duration of 3 months representing the duration of treatment as usual.

## 5. INVESTIGATIONAL INTERVENTION

### 5.1. Elements of the DBT-based group therapy

The structured skills group treatment uses elements from DBT such as psychoeducation, acceptance, mindfulness, and functional behavioral analysis, such targeting symptoms and functional problems common in ADHD. It consists of 14 weekly group sessions, each lasting two hours separated by a 15-minute break. Each group includes 7-9 patients with ADHD and two therapists. Group sessions follow a structure with manualized instruction for the therapists and workbook for the patients.

A typical session begins with introducing a new mindfulness exercise performed together in the group. The first part of the session then focuses on feedback on last week's homework of skill training, while the second part introduces a new topic and related homework for the next week. The topics for the different sessions include psychoeducation, mindfulness, functional behavioral analyses, and how to understand and manage different symptoms and aspects of ADHD, e.g. impulsivity, addiction, emotional

regulation, self-esteem, and relation to others. Interaction between the participants is important, and the therapists should encourage and balance their feedback and discussion during the session. After each group session, patients will receive 15-20 minutes of individual coaching with one of the therapists. This is an add-on element according to a Swedish adaptation of the program. The coaching focuses on adherence to homework related to each participant's situation and pre-defined goals.

## **5.2. The arm of treatment as usual condition**

The control condition of treatment as usual (TAU) was not standardized but rather defined as the clinical management/ treatment that the patient would have received if not included in the project. Some patients will be able to receive drug treatment, while others receive psychoeducation alone or in combination with medication. It could thus vary between both individuals and clinics. A survey will be made of what the patients have received from "treatment as usual" before they enter the psychotherapeutic group treatment.

## **5.3. Concomitant medication**

Treatment with the following groups of pharmacological agents will be recorded in the case report form (CRF), but is not considered as any exclusion criteria for participation. It is however recommended that the dose be kept stable during participation in the study, and for inclusion it must have been at least 6 weeks after the last dose change of drug treatment.

- ADHD medication (centralstimulants or non-stimulants)
- Other psychopharmaca

Alcohol or substance abuse will be screened for alcohol- and substance-problems; The Alcohol Use Disorder Identification Test (AUDIT) and The Drug Use Disorder Identification Test (DUDIT).

## 6. PROJECT PHASES

### 6.1. Steps with deadlines

Assignment	Deadline
Establish the project	Spring 2015
Design research protocol	Summer 2015
Application to the Regional Ethics Committee deadline	Deadline 16. August
Clarify participation from therapists in the project	Before the deadline REK application
Arrange teaching days, with introduction to the use of the manual	October/november 2015
Carry out treatment based on the manual	Start-up in November 2015 - March 2016
Analyze data and write report	2016 - 2017
Make adjustments and adapt the Norwegian version of the manual	2016 - 2017
Publication and feedback	2017

### 6.2. Phases

Phase 1:

- 1.2 Clarify roles and responsibilities between participating bodies
- 1.3 Clarify the procedure for translating the manual into Norwegian.
- 1.4 Design and secure consensus in connection with research protocols
- 1.4 Apply for REK approval

Phase 2:

- 2.1 Recruitment of patients
- 2.2 Obtain information from therapists and from patients.

Phase 3:

- 3.1 Arrange a seminar with a lecturer who has participated in the work on the Swedish manual

- 3.2 Start-up treatment, based on the Norwegian version of the manual "Psychotherapy for adults with ADHD"
- 3.3 Guidance for therapists along the way
- 3.4 Arrange a gathering for therapists midway through the treatment process

Phase 4:

- 4.1 Summary of results and feedback to participating units
- 4.2 Publishing dissemination and making available knowledge and experiences from the project
- 4.3 Give recommendations to relevant units on effective measures
- 4.4 Regional follow-up in relation to the dissemination of knowledge and competence.

### **6.3. Enrollment of patients**

Treating clinicians will ask patients whether they are interested in participation as they meet for regular appointment. Project therapists will evaluate patient eligibility and be responsible for acquiring informed consent (for either DBT, or TAU). Patients will then be given oral and written information, and asked to give permission for one of the contributing researchers to contact them.

### **6.4. Criteria for patient discontinuation**

Patients may be discontinued from study treatment and assessments at any time. Specific reasons for discontinuing a patient for this study are:

- Voluntary discontinuation by the patient who is at any time free to discontinue his/her participation in the study, without prejudice to further treatment.
- Safety reason as judged by the Principal Investigator.
- Incorrect enrollment (i.e. the patient does not meet the required inclusion/exclusion criteria for the study)
- Related Serious Adverse Event

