**Main Inclusion and Exclusion Criteria:**

- Diagnosis of ADHD assessed by a trained specialist clinician according to the Diagnostic and Statistical Manual of Mental Disorders, 4th. Edition (DSM-IV) persisting in adulthood
- Unmedicated or stably medicated with any ADHD-medication.
- Between 18 and 60 years of age (all groups).
- Exclusion criteria are any ongoing psychiatric disorders and/or

psychosocial factors considered to clearly interfere with the patients' ability to participate in the group, i.e., ongoing substance or alcohol abuse, psychotic disorder, major depressive or manic episode, and suicidal behavior; organic brain damage, neurological diseases causing mental handicap, intellectual disability ( $IQ \leq 70$ ), and pervasive developmental disorder.

- Sample Size:** Estimated 120 patients
- Efficacy Criteria:** Measures of changes in the defined outcome measures between groups and pre-post individually at follow-up.
- Safety Criteria:** In case of SAE (severe adverse events), patient will be considered for exclusion and indicated treatment will be administered immediately.

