#### **6.4.1 Procedures for discontinuation**

Patients who withdraw or are withdrawn from the study will continue clinical treatment as determined by their physician. Any reasons for withdrawing from the study will not impact the patient's clinical treatment.

Reason for discontinuation shall be recorded if reason is disclosed. The investigator is obliged to follow up any significant adverse events until the outcome is resolved.

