## **7. EFFICACY ASSESSMENTS**

### **7.1. Assessment of efficacy response**

The main aims of this study is to examine the efficacy of a manualized DBT-based group treatment compared to treatment delivered as usual for adults with ADHD on self-reported executive

functioning and emotional regulation, and secondly on core symptoms of ADHD, symptoms of depression and anxiety, and quality of life. Participants will be assessed pretreatment, after ended group-treatment or at 14-week of treatment as usual and at 6 month follow-up.

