### **10.3. Statistical analysis**

Collected data will be analyzed with SPSS (PASW statistics). Descriptive statistics is used for testing potential differences between the groups at baseline (chi-square tests for categorical variables, independent samples t-tests for continuous variables). We use independent samples t- tests to compare the mean difference of change from pre- to post-treatment between the two treatment groups, and analyses of covariance (ANCOVA) to compare these differences while adjusting for variables that differed between the groups at baseline as covariates. For the non-controlled extension part of the study, we use paired sample t-tests to assess change from baseline to 6-months follow-up, and analyses of variance (ANOVA) for repeated measures to assess change in symptom scores from baseline to post-treatment from the RCT and at 6 months follow-up after group treatment for all participants. We will estimate standardized effect sizes (ES) of the treatment by dividing the mean difference in symptom scores from pre-to post treatment with the pooled standard deviation (SD) of the respective measure, reporting as Cohen's d. The significance threshold is set at 5% (two-tailed) and we use two-sided 95% confidence intervals (CI). Analyses are restricted to participants with actual responses on each of the respective questionnaires, i.e., will exclude participants with missing values analysis-by-analysis.

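### Sections 6.4 and 6.4.1 let outcome assessment stop with study treatment, so a participant removed before week 14 can be lost from the randomised comparison; low severity and cheap to fix

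*Protocol*

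**What the plan says.** Section 6.4 puts stopping therapy and stopping measurement in one sentence: "Patients may be discontinued from study treatment and assessments at any time". Four specific reasons follow. One is the patient's own choice. The other three are in the study team's hands: "Safety reason as judged by the Principal Investigator", incorrect enrolment, and a related serious adverse event. The synopsis points the same way; after such an event the "patient will be considered for exclusion and indicated treatment will be administered immediately".

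Section 6.4.1 sets out what happens next. "Patients who withdraw or are withdrawn from the study will continue clinical treatment as determined by their physician"; the reason is recorded if it is disclosed; and "The investigator is obliged to follow up any significant adverse events until the outcome is resolved". No questionnaire is mentioned.

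The general schedule is in section 7.1: "Participants will be assessed pretreatment, after ended group-treatment or at 14-week of treatment as usual and at 6 month follow-up". Section 10.3 fixes who is analysed: "Analyses are restricted to participants with actual responses on each of the respective questionnaires", with missing values excluded analysis by analysis. Under section 10.2, group membership is announced once the draw at the site is complete, so any later removal is made with the arm known.

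**The concern.** Stopping a treatment and stopping measurement are different events, and a randomised comparison stays intact only if the first does not bring the second with it. Section 6.4 joins them, and 6.4.1 does not separate them again. A participant whom the team removes before week 14, and who would have been willing to fill in two questionnaires, can therefore end with no primary outcome. Section 10.3 then leaves that person out.

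Who is still measured is a rule of conduct, and this protocol sets it in section 6.4. A statistical analysis plan can choose how to treat a missing score but cannot collect one.

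The loss biases the comparison only if removals differ between arms in number or kind. That is possible. In the DBT arm, "After each group session, patients will receive 15-20 minutes of individual coaching with one of the therapists", on top of the weekly session, whereas section 5.2 describes usual treatment as differing from person to person and clinic to clinic. A safety or eligibility problem may have more occasions to be noticed in the DBT arm. This is an inference; the protocol reports no removal rates for either arm.

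**Working it through.** **Inputs.** Difference 10, SD 15, two-sided alpha 0.05, power 0.90, dropout up to 20%, total 120 (sections 10.1 and 10.3); 1:1 allocation (section 10.2), so 60 per arm. Assumed, because the protocol gives no figure: k = 1, 2 or 3 study-team removals, all in one arm, all before week 14 and all unmeasured.

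**The plan's own figure.** n per group = 2 × (1.960 + 1.282)² × 15² / 10² = 47.3, so 48, or 49 with the t distribution. This agrees with the stated figure of about 50. Allowing for dropout, 48 / 0.8 = 60 per group, 120 in total. The sample size is sound and is not in question.

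**Size of the bias.** If removed participants end g points worse than stayers in the same arm, the available-case mean of that arm is off by (k/60) × g.

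*Case A: removals from the DBT arm.* Stayers are 10 better than usual treatment and removed participants end at the usual-treatment mean (g = 10). The all-randomised difference is 10 × (1 − k/60).

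*Case B: removals from the usual-treatment arm.* Removed participants end 10 worse than stayers in that arm (g = 10). The all-randomised difference is 10 + 10 × k/60.

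The available-case estimate is 10 in both cases.

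| k | A: all-randomised difference | 10 overstates it by | B: all-randomised difference | 10 understates it by |
|---|---|---|---|---|
| 1 | 9.83 | 1.7% | 10.17 | 1.6% |
| 2 | 9.67 | 3.4% | 10.33 | 3.2% |
| 3 | 9.50 | 5.3% | 10.50 | 4.8% |

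*Case C: no true effect.* DBT removals end 1 SD (15 points) worse than stayers. The false difference is k/60 SD = 0.017, 0.033 or 0.050 SD, that is 0.25, 0.50 or 0.75 point. With 60 − k against 60 analysed, the two-sided error is 5.1%, 5.4% or 5.8%.

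**Scale.** The 95% half-width for a difference with 60 per arm is about 1.98 × 15 × √(2/60) = 5.4 points. With 48 per arm it is about 6.1. The shifts above are at most about a seventh of that (0.75 / 5.4 = 0.14).

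**Power if the scores are collected and the estimate is the smaller one in case A** (two-sample t test):

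| Scored per arm | 10 | 9.83 | 9.67 | 9.50 |
|---|---|---|---|---|
| 60 | 95.2% | 94.5% | 93.8% | 93.1% |
| 48 | 89.8% | 88.9% | 87.8% | 86.7% |

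**The case against.** The strongest reply is that the wording is permissive and the numbers are negligible. Section 6.4 says that assessments may stop, not that they must. Section 7.1 schedules participants at week 14 without exempting those who stop treatment. Section 9.1 requires the reason for any omitted assessment to be noted. Section 12.3 guarantees the right to refuse further participation, so some sentence allowing assessments to end is needed. Detection of problems is not confined to the DBT sessions: section 8 tells every patient to contact the investigator about serious symptoms, and the reporting rules are the same in both arms. Eligibility is judged at screening, before the draw, so late findings of incorrect enrolment should be few and should rest on entry criteria rather than outcome.

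Most of this stands, and it sets the severity. It does not close the gap. Section 7.1 speaks of participants in general, while 6.4 is the specific rule and expressly allows assessments to end. Section 9.1 records why a score is absent but does not obtain it. The right to refuse covers those who refuse, not those whom the team removes.

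A reader might infer more than the text supports:

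- *That everyone who leaves the groups is lost.* Someone who only stops attending is still due under 7.1, and someone removed after the 14-week visit already has the scores.
- *That the 20% dropout allowance measures the problem.* If all lost DBT participants gained nothing, 10% or 20% loss would turn a difference of 10 into 9 or 8. But that allowance covers dropout of every kind, and the protocol does not attribute it to study-team removal.
- *That the bias favours DBT.* Cases A and B point in opposite directions, and for incorrect enrolment no direction can be argued at all.
- *That power is threatened.* The 20% allowance leaves 48 per arm and about 90% power.

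**Conclusion.** The point holds in a limited form. Sections 6.4 and 6.4.1 allow a randomised participant whom the study team removes before week 14 to go without BRIEF-A and DERS, and section 10.3 then drops that person from the primary comparison. The number affected is unknown and the direction of any bias is unknown.

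On the assumption of 1 to 3 removals out of 60, all in one arm and ending 10 points worse than stayers, the planned difference of 10 is misstated by no more than about 0.5 point (0.75 point if they end a full SD worse). Both are small against a half-width of about 5.4, and the bias is zero if removals are equal in number and kind. Severity is low. The reason to act is that the scores cannot be recovered later and cost little to collect.

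**What to change.** In sections 6.4 and 6.4.1 add:

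> Stopping study treatment, or removal from it by the study team, does not end study assessments. Unless the participant withdraws consent to assessment, BRIEF-A and DERS are collected 14 weeks after the start of the allocated condition and included in the comparison under the arm drawn.

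The collection clause is the essential part, because only the protocol can secure it. The clause on the arm drawn could sit in the statistical analysis plan instead.

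The cost is one extra questionnaire round per affected participant and possibly a slightly smaller estimated effect. Sample size and design do not change.

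Two additions are optional and not needed for the randomised comparison. The first is a 6-month round for removed participants. That phase is an uncontrolled extension timed from the end of DBT, so a date would have to be defined for a usual-treatment participant removed before starting DBT. The second is rewording the synopsis so that a serious adverse event leads to considering an end to study treatment rather than exclusion.

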#### **6.4.1 Procedures for discontinuation**

Patients who withdraw or are withdrawn from the study will continue clinical treatment as determined by their physician. Any reasons for withdrawing from the study will not impact the patient's clinical treatment.

Reason for discontinuation shall be recorded if reason is disclosed. The investigator is obliged to follow up any significant adverse events until the outcome is resolved.

## **7. EFFICACY ASSESSMENTS**

### **7.1. Assessment of efficacy response**

The main aims of this study is to examine the efficacy of a manualized DBT-based group treatment compared to treatment delivered as usual for adults with ADHD on self-reported executive

functioning and emotional regulation, and secondly on core symptoms of ADHD, symptoms of depression and anxiety, and quality of life. Participants will be assessed pretreatment, after ended group-treatment or at 14-week of treatment as usual and at 6 month follow-up.

#### Primary Outcome(s)

1. Change in executive function impairments (total and separate dimensional scores) assessed by the self/informant-reports of adults aged Behavior Rating Inventory of Executive Function (BRIEF-A) at end of 14-weeks group treatment, and after 6 months post-treatment, compared to baseline and treatment as usual as control treatment strategy
2. Change in emotional regulation (total and separate dimensional scores) assessed by the self/informant-reports Difficulties in Emotion Regulation Scale (DERS) at end of 14-weeks group treatment, and after 6 months post-treatment, compared to baseline and treatment as usual as control treatment strategy

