# PROTOCOL SYNOPSIS

## Effects of structured skills training group in treatment of Attention Deficit Hyperactivity Disorder in adults

A growing number of adults are diagnosed with Attention-Deficit Hyperactivity Disorder, or ADHD. People with ADHD can have problems in paying attention, feeling restless or hyperactive and behaving impulsively. Pharmacological (drug) treatments are well established, but a significant number of patients does not respond well or experience adverse effects, which results in stopping the treatment. Furthermore many patients request for psychological treatment to help them with symptoms that are not resolved by simply taking drugs.

Structured group therapy has shown improvement of symptoms among patients with other psychiatric conditions. Although still inconclusive, some studies have indicated that structured skills training groups are beneficial for adult patients with ADHD in outpatient psychiatric units, reducing ADHD symptoms in people who remained stable regarding their medication status.

This study aim to investigate the potential effects of structured skills training groups in a clinically relevant but still controlled setting, and whether they help alleviate symptoms and improve quality of life for adult ADHD patients. This trial examines effects of Dialectical Behavioral Therapy-based group treatment (DBT-bGT) on the broader and clinically relevant executive functioning and emotional regulation in adults with ADHD

By use of a controlled design, adult patients with ADHD will be randomly assigned to receive either weekly DBT-bGT or treatment as usual (TAU) during 14 weeks therapy period. Subsequently, participants receiving TAU will also be offered the supplementary DBT-bGT. All participants will be reassessed at a follow-up visit six months after ended DBT-bGT.

Primary outcomes are the Behavior Rating Inventory of Executive Function (BRIEF-A) and the Difficulties in Emotion Regulation Scale (DERS). Secondary outcomes include self-reported ADHD-symptoms, depressive and anxiety symptoms, and quality of life assessments.

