# **10. STATISTICAL CONSIDERATIONS**

## **10.1. Determination of sample size**

To assess the required number of participants, a power analysis was calculated on the basis of literature indicating the similar DBT-group intervention in a smaller study showed a significant reduction in ADHD measures in the skills training group (n=19) compared to the control group (n=18) (Hirvikoski et al 2011). To address the hypothesis of superiority of the DBT-based group treatment on different outcome measures and an assumed difference in at least 10% between means (and SD 15%) of the two independent groups, we estimated a need of sample size of about 50 participants in each group (alpha = .05, power = .9) (<https://clincalc.com/stats/samplesize.aspx>). To account for dropouts up to 20%, more patients are needed, resulting in a total of 120 participants.

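### The primary outcome spans two instruments, all their scores, two raters and two time points at an unadjusted 5%, and no rule says what counts as success

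*Protocol*

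**What the plan says.** The synopsis names two instruments: "Primary outcomes are the Behavior Rating Inventory of Executive Function (BRIEF-A) and the Difficulties in Emotion Regulation Scale (DERS"). The list of primary outcomes in section 7.1 then widens each of them.

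- **Scores and raters, BRIEF-A:** "Change in executive function impairments (total and separate dimensional scores) assessed by the self/informant-reports".
- **Scores and raters, DERS:** "Change in emotional regulation (total and separate dimensional scores) assessed by the self/informant-reports".
- **Times and comparators, both instruments:** "at end of 14-weeks group treatment, and after 6 months post-treatment, compared to baseline and treatment as usual".

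The opening of section 7.1 is narrower on the rater. It describes efficacy "compared to treatment delivered as usual for adults with ADHD on self-reported executive" functioning and emotional regulation, and does not mention informants.

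Section 10.3 sets one threshold for all tests: "The significance threshold is set at 5% (two-tailed) and we use two-sided 95% confidence intervals (CI"). Its between-group test is a t-test to "compare the mean difference of change from pre- to post-treatment between the two treatment groups", with ANCOVA as the adjusted version. It assigns the 6-month data to a non-controlled extension, analysed by paired t-tests and repeated-measures ANOVA.

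Section 10.1 sizes the trial with one calculation at alpha 0.05 and power 0.9. Its stated purpose is broader: "To address the hypothesis of superiority of the DBT-based group treatment on different outcome measures".

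**The concern.** A primary outcome should let a reader know before the data are seen which result would make the trial positive. Here the definition covers two instruments, an unstated number of scores on each, one or two raters and two time points. The protocol does not say whether one instrument is enough or both must succeed, and it gives no testing order and no division of the 5%. A single favourable dimension score could therefore be reported as a primary success, and nobody could tell it from a result picked afterwards.

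Two internal conflicts add to this.

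- **Rater.** The aim is self-report, while the outcome list says self/informant.
- **6 months.** The outcome list promises a comparison with TAU. Sections 3.2 and 4 say that TAU participants are offered the group treatment after the first 14 weeks, and section 10.3 tests this time point without a control. The promised comparison has no analysis behind it.

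**Working it through.** **Inputs.** From section 10.1: difference 10, SD 15 (so d = 10/15 = 0.667), alpha 0.05, power 0.90, dropout 20%, total 120. From section 10.3: two-sided 5%, one threshold. The correlation between scores and the number of dimension scores are not given, so correlations of 0, 0.5 and 0.8 are assumed.

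**1. Reproduce the sample size.** n per arm = 2 × (1.960 + 1.282)² × 15² / 10² = 47.3, so 48. The t-based value is 48.3, so 49. Both agree with the stated figure of about 50. Then 2 × 48 / (1 − 0.20) = 120, the stated total. One-sided testing would give 39 per arm and 80% power would give 36, so the calculation is for one two-sided comparison at 5%. It is sound for that, and it leaves 120 × 0.80 / 2 = 48 evaluable per arm.

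**2. Count the randomised tests.** Only week 14 has a between-group test. The smallest family is two: one total score per instrument, one rater. If informant reports are also analysed, it is four. Dimension scores add an unknown number.

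**3. Family-wise error at an unadjusted 5%.** For k independent tests it is 1 − 0.95^k. For k = 2 this is 1 − 0.9025 = 9.75%. For correlated tests it is 1 − P(all |Z| ≤ 1.96) under an equicorrelated normal model, by numerical integration.

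| Tests | Independent | r = 0.5 | r = 0.8 |
|---|---|---|---|
| 2 (two totals, one rater) | 9.8% | 9.1% | 7.8% |
| 4 (two totals, both raters) | 18.5% | 15.6% | 11.4% |
| 8 (assumed count, illustration only) | 34% | 25% | 16% |

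Every entry exceeds 5%, including the smallest family at high correlation.

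**4. Power once the error is controlled** (48 per arm, d = 0.667, no allowance for therapy-group clustering).

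- One test at 5%: 89.8% (t-based), 90.4% (normal).
- One test at 2.5%, the first Holm step: 83.7% (t-based), 84.7% (normal). A given outcome has this power when the other has no effect, apart from the rare case where that other test is falsely significant.
- Holm with the assumed effect on both, independent outcomes, normal approximation: 0.847 + (0.904 − 0.847) × 0.847 = 0.895. The bracket is the chance that an outcome passes at 5% but not at 2.5%. It is rescued when the other passes at 2.5%.
- The same by simulation at correlations 0.5 and 0.8: about 89% and 88%.
- Both required, each at 5%, independent: 0.904² = 82% joint power, rising with correlation.

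**The case against.** The strongest reply is that the protocol nowhere says that one success suffices. A reader might infer an any-one-wins rule from the list of primary outcomes, but no section states it. The instruments are listed together, and a both-must-succeed reading of the two totals would need no alpha split. This stands: the fault is the absence of a success rule, and the error rates above describe what the text permits, not what it declares.

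Three further readings are tempting and go too far.

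- **A very large error rate.** Assuming 8 to 19 primary scores gives 25–41% at correlation 0.5 and 34–62% if independent. The protocol gives no such count, and independence is implausible for subscales of one instrument. These figures only illustrate.
- **Two time points double the family.** The 6-month tests are uncontrolled before-after tests. They are not further randomised comparisons, and their fault is the missing comparison with TAU.
- **Correction costs 6 points of power on each outcome.** The 84% is the first-step figure. Holm recovers most of the loss when both outcomes respond.

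The wording on raters may merely describe the available forms, so it multiplies tests only if both are analysed. It must still be reconciled with the self-report aim.

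Finally, multiplicity is often settled in an SAP, which is not at hand, and section 10.3 does not exclude an adjustment. That lowers certainty about what will be done. It does not remove the point, because the protocol itself makes every score primary and itself fixes the threshold. An SAP that narrowed the definition would depart from the protocol.

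**Conclusion.** The point holds and should be settled before outcome data are analysed. The protocol defines the primary outcome too broadly, sets one unadjusted two-sided 5% threshold, and states no success rule, order or alpha split. It also contradicts itself on the rater and promises a 6-month comparison with TAU that its own analysis section does not provide.

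The size that can be defended from the text is a family-wise error of about 9–10% for the two totals at week 14, or 7.8% at correlation 0.8. This assumes one rater and that success on either would be claimed. Anything larger depends on both raters being analysed or on an assumed number of dimension scores. The sample-size arithmetic is correct for a single comparison, but the protocol does not say which comparison that is.

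**What to change.** Reword the primary outcomes and section 10.3 as follows.

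1. Two primary endpoints: self-reported BRIEF-A total and self-reported DERS total, change from baseline to week 14, DBT-based group treatment against TAU.
2. Test both with Holm at overall two-sided 5%: the smaller p-value against 2.5% and, if it passes, the other against 5%. Alternatively, state that both must succeed, each at 5%.
3. Make dimension scores, informant reports and the uncontrolled 6-month assessments secondary, without confirmatory claims. Delete the 6-month comparison with TAU from the primary outcomes.
4. Restate the power in section 10.1 at 48 evaluable per arm and d = 0.667, before any allowance for therapy-group clustering: about 84% per outcome at the 2.5% step (worst case, only one outcome affected), and about 88–90% per outcome under Holm if both have the assumed effect.

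The cost is wording, a slightly stricter threshold, and about 1 to 6 points of power per outcome (from about 90% to between 84% and just under 90%). No extra participants are needed if that is accepted. Keeping 90% at the 2.5% step would take 56 per arm, or 2 × 56 / 0.80 = 140 in total. Requiring both avoids the alpha split but lowers the chance of overall success to about 82% if the outcomes are independent.
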